#### **9.7.3.2 Analysis of Treatment Data**

Analysis of treatment data is part of the analysis of exploratory objectives, presented in section [9.7.3.4](#).

#### **9.7.3.3 Analysis of Primary Endpoint**

The primary objective will only be assessed in users with the long-term treatment (>12 months) and where z-scores of lumbar spine, total hip, or femoral neck are available. For rates of events of BMD z-scores below the age-related threshold of -2 standard deviations, the number and percentage of patients with these events will be provided including 95% CIs.

The aggregated number, frequency of DXA scans, anatomic site of DXA scan, machine type, and imaging parameters of DXA scans during the observational period will be analysed by descriptive statistics. If results of DXA scans can be interpreted in a categorised way, shift tables for the change from baseline, will be provided, where available. If images of the DXA scans can be provided by the doctors, they will be reviewed by 1 independent expert for their suitability and included in an additional sensitivity analysis.

Sensitivity analyses using different criteria (e.g., machine type) to select DXA scans that ensure their comparability will be performed to evaluate the primary endpoint if the sample size allows (e.g., if more than 30 patients remain after selection of suitable cases) and will be further detailed in the SAP.

#### **9.7.3.4 Analysis of Exploratory Endpoints**

For incidence rates of osteoporosis or suspected osteoporosis-related bone fractures, the number and percentage of patients with fractures will be provided including 95% CIs.

The frequency of laboratory assessments of liver enzyme levels will be analysed by descriptive statistics. Laboratory values of liver enzyme levels will be assessed by means of descriptive statistics at each assessment time and by absolute and relative changes to

baseline. For rates of AEs indicative for liver injury and of liver enzyme elevation, the number and percentage of patients with these events and the total number of events as well as the EAIR (exposure adjusted incidence rate) will be provided including 95% CIs. A preliminary list of included liver enzyme elevation events is provided as a stand-alone document (see section 15.1), with complete specification to be done in the SAP based on the MedDRA coding system version available at the time of statistical analysis. The incidence rates, as well as the number and percentage of patients, are also presented for the subgroup of patients in whom the AEs were categorised as ADRs.

For rates of AEs indicative for mood disorders, the number and percentage of patients and the total number of events as well as the EAIR will be provided including 95% CIs. Events including the PTs mood swings, affect lability, emotional disorder, irritability, mood altered, anxiety, bipolar disorder, mania, depression, depressed mood will be specified in the SAP based on the MedDRA coding system version available at the time of statistical analysis. The incidence rates, as well as the number and percentage of patients, are also presented for the subgroup of patients in whom the AEs were categorised as ADRs.

For rates of uterine endometrial adenocarcinoma events and mammary gland adenocarcinoma events, the number and percentage of patients with each of these event categories and the total number of events in each category as well as the EAIR will be provided including 95% CIs for each category. Events contained in each category will be specified in the SAP based on the MedDRA coding system version available at the time of statistical analysis.

Summary statistics for the treatment duration will be provided. The dosing regimen patterns and reasons for dosing regimen switch will be evaluated by descriptive statistics. Summary statistics will be provided for incidences and reasons for dosing regimen interruption or premature discontinuation of Yselyt® and/or ABT. A transition table will be provided to compare prescribed baseline regimens with prescribed end of study regimens.

For reported adherence to the prescribed treatment, documented deviations from the prescribed dosing regimen will be evaluated by descriptive statistics.

For rates of AEs regarding cardiac disorders (ventricular arrhythmias [e.g., ventricular tachycardia and ventricular fibrillation], cardiac arrest, and sudden cardiac death) indicative of potential QT prolongation, the number and percentage of patients with these events and total number of events as well as the EAIR will be provided including 95% CIs. Events indicative of potential QT interval prolongation will be specified in the SAP based on the MedDRA coding system version available at the time of statistical analysis. Number and percentage of patients with QT interval prolongation as reported by physicians following ECG measurement will be evaluated by descriptive statistics. The incidence rates, as well

---

Additional analyses on ADRs will be performed. Considered as special situations in this study. See definition at end of this section.

as the number and percentage of patients, are also presented for the subgroup of patients in whom the AEs were categorised as ADRs.

Frequency of DXA scans in defined time periods (see section 9.1.2) and frequency of DXA scans prior to treatment initiation in patients with risk factors for osteoporosis and bone loss will be evaluated by descriptive statistics. The results will also be displayed stratified by dose (100mg/100mg + ABT/200mg + ABT)

Number and percentage of patients with an initial treatment dose of 200 mg without ABT that are not treated with ABT after  $\geq 6$  months,  $\geq 9$  months,  $\geq 12$  months,  $\geq 15$  months (continuing at 3-month intervals) while continuing a 200 mg dose of Yselty® will be evaluated by descriptive statistics.

For ADRs and SADR, the incidence as well as EAIR, will be provided including 95% CIs on MedDRA system organ class (SOC) and preferred term (PT) level.

BMD will be displayed as absolute and relative change in density ( $\text{g}/\text{cm}^2$ ) and absolute value and relative change of z-scores and t-scores over time by means of summary statistics; e.g., DXA scans performed at baseline (if available) vs. timepoint 1 – 1st year (+/-6 months) after treatment initiation, timepoint 1 – 1st year (+/-6 months) after treatment initiation vs. DXA scans performed at timepoint 2 – 2nd year (+/-6 months), where the measurements are at least 6 months apart. This is continued in the same way for further years if the sample size is at least 5 patients. Changes are only analysed if e.g., the machine types, the location of the scan and other criteria that allow comparability are consistent. A subgroup analysis of t-scores for the subgroup of postmenopausal patients and of z-scores in the subgroup of premenopausal patients will be conducted, if sample size allows. Additionally, patients who experienced BMD decrease during the study but continued to be observed in the study, regardless of the reason for which Yselty® treatment was discontinued, will be investigated as a separate subgroup. This subgroup analysis will include the presentation of both absolute value and relative change of z-scores and t-scores after discontinuation. If the sample size permits, this subgroup will be stratified based on whether alternative treatments administered after discontinuation may also lead to a decrease in BMD (refer to “previous systemic treatments” in section 9.3.3).

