## **9 Research Methods**

### **9.1 Study Design**

This is a non-interventional, prospective, multicentre, multinational, cohort study based on primary data collection. Approximately 1,000 patients with documented uterine fibroids and symptoms such as HMB and with long-term Yselty® treatment in accordance with the SmPC will be included.

The study will be conducted in 5 European countries (Germany, Italy, Spain, Poland, and the UK), whereas the selection and sequence of countries may vary depending on the launch dates of Yselty®. For each country included in the study, the study start will be defined as after Yselty® has been authorised and made commercially available in that country. It is planned that Germany will be the first country to launch. The scheduled total study duration per country includes a recruitment phase of up to 18 months and an individual prospective observational period per patient for as long as feasible within the scheduled study timeframe. In case the observational period per country is prolonged, the data collection will be prolonged as well. The number of follow-up visits as per routine clinical practice for an individual patient will be dependent on the individual prospective observational period and are expected to be approximately every 12 months for this patient population. Visits to assess response to treatment will be more frequent at the beginning, and further visits may be required (depending on the country) to renew prescriptions approximately every 3 months.

Treatment with Yselty® will follow the physician's prescription according to the recommendations given in the SmPC. All decisions on therapeutic or diagnostic procedures, treatments, management of the indication, or resource utilisation will be at the full discretion of the treating physician without interference by the sponsor/MAH (referred to as MAH in the rest of this document) or study protocol. All treatment decisions will follow the real life treatment behaviour.

The assessment of BMD by DXA scans will be done as per routine clinical practice. For patients who received ABT from the initiation of Yselty®, the study results regarding BMD assessment will be contextualised with the real-world data available from literature for Ryeqo® at the time of the reports.

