### 9.1.2 Endpoints

The primary endpoint of objective **I**. is only assessed in patients with long-term treatment (>12 months) and is:

- Number and proportion of patients with a lumbar spine, total hip, or femoral neck BMD z-score below the threshold of -2 standard deviations.

The exploratory endpoints of this study are:

- For objective **II.a**:
  - Incidence rate of osteoporosis or fractures suspected to be due to osteoporosis; all suspected osteoporotic fractures (minimal- or non-traumatic) of long bones or spine where the physicians suspect an osteoporotic cause of the fracture
- For objective **II.b**:
  - Number and proportion of patients with elevated liver enzyme levels above the upper limit of normal
  - Incidence rate of adverse events suggestive of liver injury or related to liver enzyme elevation
- For objective **II.c**:
  - Incidence rate of adverse events regarding mood disorders including mood swings, affect lability, emotional disorder, irritability, mood altered, anxiety, bipolar disorder, mania, depression, depressed mood
- For objective **II.d**:
  - Incidence rate of uterine endometrial adenocarcinoma events
  - Incidence rate of mammary gland adenocarcinoma events

---

Additional analyses on ADRs will be performed.

 The RMP (see section 15.1) contains targeted follow-up questionnaires for these events. Physicians who report these events will be asked to fill the corresponding targeted follow-up questionnaire.

 The RMP (see section 15.1) contains targeted follow-up questionnaires for these events. Physicians who report these events will be asked to fill the corresponding targeted follow-up questionnaire.

 A list of MedDRA terms for hepatic events is available as a stand-alone document (see section 15.1).

- For objective **II.e**:
  - Number and proportion of patients starting each Yselyt® dosing regimen, time spent on each dosing regimen, and changes in dosing regimens
- For objective **II.f**:
  - Patient adherence to prescribed treatment, including ABT
- For objective **II.g**:
  - Incidence rate of adverse events for cardiac disorders (ventricular arrhythmias [e.g., ventricular tachycardia and ventricular fibrillation, flutter, torsade de points], cardiac arrest, and sudden cardiac death) suggestive of potential QT interval prolongation

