### **9.3.6 Variables to Assess the Exploratory Endpoints**

The variables for the exploratory endpoints are:

- For objective **II.a**:
  - Osteoporosis diagnoses
  - Bone fracture events (long bones, spine)
  - For fractures, the probability of an osteoporotic cause of the fracture judged by the physician
  - Laboratory values of 25-hydroxy vitamin D, if available
- For objective **II.b**:
  - Laboratory values of liver enzyme levels or values indicative of liver injury such as alanine aminotransferase (ALT), aspartate aminotransferase (AST), bilirubin, gamma-glutamyl transferase (GGT), and alkaline phosphatase (ALP), if available
  - Date of laboratory assessment of liver enzyme levels, if performed
  - Elevated liver enzyme events
  - Events indicative of liver injury
- For objective **II.c**:
  - Mood disorder events of mood swings, affect lability, emotional disorder, irritability, mood altered, anxiety, bipolar disorder, mania, depression, depressed mood

- For objective **II.d**:
  - Uterine endometrial adenocarcinoma events
  - Mammary gland adenocarcinoma events
- For objective **II.e**:
  - Yselty® dosing regimen and changes in dosing regimens (see section 9.3.4)
- For objective **II.f**:
  - Reported patient adherence to prescribed treatment, including use of ABT
- For objective **II.g**:
  - Cardiac disorder events (ventricular arrhythmias [e.g., ventricular tachycardia and ventricular fibrillation, flutter, torsade de points], cardiac arrest, and sudden cardiac death) suggestive of potential QT interval prolongation
  - ECG findings indicative of QT interval prolongation, according to the physician's information
- For objective **II.h**:
  - DXA scan in defined time periods; Yes/No (see section 9.1.2)
  - DXA scan prior to treatment initiation in patients with risk factors for fractures, osteoporosis, or bone loss; Yes/No
  - Prescription of 200 mg Yselty® without concomitant ABT in defined time periods; Yes/No (see section 9.1.2)
- For objective **II.i**:
  - ADRs
  - SADR
- For objective **II.j**:
 

For patients with multiple DXA scans (at baseline and/or follow-up[s]):

  - BMD z-score and BMD t-score measured in lumbar spine, total hip, or femoral neck
  - Absolute value of density (g/cm^2)
  - Date of DXA scan, if performed
  - Anatomic site of DXA scan, machine type, imaging parameters of DXA scan, and reference population used, if available

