### **9.7.2 Study Population**

All analyses will be performed for the total study population (overall analysis). Separate analyses for each participating country will be provided if patient numbers are sufficient and if required for local reasons. In addition, data will be stratified whenever reasonable and dependent on the number of patients by the following parameters: country, age, race, dosing regimen, long- vs. short-term use of Yselyt®, and other relevant clinical characteristics and will be specified in the SAP.

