## **9.9 Limitations of the Research Methods**

Possible limitations of the study are based on the observational design and the fact of voluntary participation of physicians and patients. Physicians and patients who voluntarily agree to participate in this study might differ from those who do not agree. Consecutive enrolment should avoid any selection bias and increase the likelihood of representativeness.

Although the study aims to include participants from a variety of geographic regions, there may be local limitations that reduce the representativeness of patients recruited, such as

patient access to recruiting physicians (including differences in patient profile in specialized, recruiting sites vs local general practice), Yselty® availability and reimbursement, and decisions relating to local standard of care.

The main objective depends on two factors that are crucial but beyond the control of the study: First, the overall uptake of Yselty® and the proportion of patients treated beyond 12 months. Second, the extent to which doctors perform DXA scans after 1 year (as recommended in the SmPC) as part of their routine care. Depending on the country, this could be either facilitated or hindered by the reimbursement status of DXA scans.

BMD measurements, the primary objective, have a good reproducibility under highly controlled conditions, but such conditions do not generally apply in clinical practice. Many factors could affect the accuracy of BMD testing, including inter-machine variance as well as the experience of the operator. In addition, a high rate of missing BMD measurements at week 24 and week 52 due to study discontinuations was observed in the two pivotal studies [11]. This indicates that BMD assessment may become difficult due to the low number of observations recorded, especially for long-term users which are of special interest in this study. When interpreting the proportion of patients with z-scores below -2 standard deviations indicating loss of bone density, it should be kept in consideration that normalisation of z-scores is usually based on BMD measurements for a single bone. If multiple measurements have been taken in a patient, the likelihood of results being below threshold increases with the number of bone sites examined for each patient.

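### The planned analysis of endpoint II.a reports only fractures and names no rate; if osteoporosis without fracture is counted over the whole cohort, the result is a lower bound that depends on DXA uptake

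*Protocol*

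**What the plan says.** Section 9.1.2 sets the endpoint for objective II.a: "Incidence rate of osteoporosis or fractures suspected to be due to osteoporosis". Section 9.3.6 lists "Osteoporosis diagnoses" as a variable of its own, next to fracture events and the physician's judgement of an osteoporotic cause. It gives no diagnostic criterion and no link to a scan.

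The analysis in 9.7.3.4 begins "For incidence rates of osteoporosis or suspected osteoporosis-related bone fractures, the number and percentage of patients", and the same sentence ends by saying that "the number and percentage of patients with fractures will be provided including 95% CIs". No EAIR is named for II.a. The paragraphs that follow name an EAIR with 95% CI for liver, mood, cancer and cardiac events, and for ADRs and SADRs.

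On the population, 9.7.2 states: "All analyses will be performed for the total study population (overall analysis". Nothing in 9.7.3.4 restricts II.a further. The primary endpoint, by contrast, is analysed in 9.7.3.3 only in long-term users and "where z-scores of lumbar spine, total hip, or femoral neck are available".

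On scanning, 9.1 says: "The assessment of BMD by DXA scans will be done as per routine clinical practice". Under 9.1.2 (II.j) a baseline scan is recommended only for women at high risk of osteoporosis or bone loss. Section 9.9 names as a factor beyond the study's control "the extent to which doctors perform DXA scans after 1 year (as recommended in the SmPC) as part of their routine care", and adds that reimbursement may help or hinder it by country.

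**The concern.** The endpoint and its analysis do not match. The endpoint has two components and is a rate. The analysis has one component in its numerator and gives a percentage. A table built to the letter of 9.7.3.4 would not answer objective II.a.

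Repairing this by adding osteoporosis diagnoses to the numerator exposes a second weakness. A woman never scanned is unlikely to be given a diagnosis of osteoporosis without fracture, yet under 9.7.2 she stays in the denominator as a non-case. The missing-data rule in 9.7.1 (no imputation, missing shown as a category) does not clearly catch her, because a condition nobody looked for leaves no blank field.

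Either way the II.a result errs in the reassuring direction, on the safety question this study exists to address. Differences between countries or regimens could also reflect scan uptake rather than bone health.

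**Working it through.** **Step 1: endpoint against analysis.**
- Section 9.1.2: osteoporosis or suspected osteoporotic fracture; incidence rate.
- Section 9.7.3.4, opening of the sentence: both components; incidence rates.
- Section 9.7.3.4, statistic actually provided: patients with fractures; number and percentage with 95% CI; no EAIR.

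The sentence is inconsistent within itself as well as with 9.1.2. Two readings follow: (A) literal, so non-fracture osteoporosis is not in the II.a numerator; (B) a drafting slip, so diagnoses are meant to be counted, over the total population.

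**Step 2: the plan's own figures.** The protocol gives no expected value or precision for II.a. Its only precision figures are in Table 2, for the primary endpoint. With half-width = 1.96 × √(p(1 − p)/n) and p = 0.025:
- n = 800: 1.08% (Table 2: 1.10%)
- n = 640: 1.21% (1.20%)
- n = 512: 1.35% (1.35%)
- n = 409: 1.51% (1.50%)

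Table 2 reproduces. Its sample sizes allow for dropout only and carry no information on how many women are scanned.

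**Step 3: direction under reading B.** Let f be the share with a fracture (seen in all women), π the share with osteoporosis without fracture (assumed to be seen only if scanned), and c the share scanned. With scanning unrelated to risk,

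whole-cohort percentage = f + π × c, against a true f + π.

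The documents give none of the three. Illustrative values, all assumed, with π = 2.5%:
- f = 0 (true 2.5%): c = 80% gives 2.0%, c = 50% gives 1.25%, c = 30% gives 0.75%.
- f = 0.5% (true 3.0%): c = 80% gives 2.5%, c = 50% gives 1.75%, c = 30% gives 1.25%.

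The non-fracture part shrinks in proportion to c; the fracture part does not move. That last statement applies during treatment and the 30 days after it. Beyond that, under 9.2.6 and 11.3, follow-up continues only for women with BMD decrease or osteoporosis.

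**Step 4: would a scanned-only denominator be right?** Assume 20% of women are high-risk with risk ratio 3, the overall true value is 2.5%, and 90% of high-risk and 20% of other women are scanned.
- Risk in other women: 0.025/(0.2 × 3 + 0.8) = 1.786%; in high-risk women: 3 × 1.786% = 5.357%.
- Coverage: 0.2 × 0.9 + 0.8 × 0.2 = 0.34.
- Detected: 0.18 × 5.357% + 0.16 × 1.786% = 1.25% of the cohort.
- Scanned-only: 1.25%/0.34 = 3.68%.

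Here the whole-cohort figure is half the truth and the scanned-only figure about 1.5 times the truth. If 60% of both groups were scanned, the scanned-only figure would return 2.5%. Neither denominator is safe alone.

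**The case against.** The best defence has four parts.

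*The text plans a fracture percentage, which does not depend on DXA.* Correct on reading A. No diluted osteoporosis percentage is then planned, but the endpoint loses a component, so the defect changes form without going away.

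*The information appears elsewhere.* Section 9.7.3.5 gives incidence and EAIR for all AEs by preferred term, so an osteoporosis diagnosis recorded as an AE would appear there. Scan frequency is reported under 9.7.3.3 and II.h, the latter also by dose. The primary endpoint is restricted to women with a z-score, and 9.7.4 and 9.9 disclose misclassification and scan uptake. All this stands. But an AE listing by preferred term is not the II.a endpoint, has the same ascertainment limit, and nothing ties scan coverage to II.a. The checklist in 15.2 itself answers no on validity of outcome measurement (6.3) and on analytic control of outcome misclassification (10.6).

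*Table content belongs to the SAP.* In general yes. But 9.7.3.4 itself fixes the II.a statistic, and fixes one that differs from 9.1.2.

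*The size is unknown.* This stands in full. A reader might infer from Table 2 that the osteoporosis percentage is 20% too low, because 200 of 1,000 women leave before month 12, or multiply 0.80 by assumed uptakes of 70%, 50% and 30% to reach understatements of 44%, 60% and 76%. The documents support neither. Table 2 describes dropout, not detection. The sum ignores earlier scans in high-risk women and any fractures in the composite, supposes that early leavers carry the same burden as those who stay, and treats scanning as unrelated to risk. It is likewise too strong to say that osteoporosis can be found only by DXA, since the protocol collects physician diagnoses without a criterion.

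**Conclusion.** The concern holds in a limited form. The mismatch between 9.1.2 and 9.7.3.4 (a component missing from the numerator, no EAIR) is plain from the text and needs no assumption. The ascertainment point is conditional: if osteoporosis diagnoses are counted over the total population, the percentage is a lower bound for the non-fracture component. This rests on the inference that such osteoporosis is mostly recognised through DXA, and on the protocol's own statements that scanning is routine, risk-related at entry and outside its control. The direction is secure on that inference. The size is not derivable, and the halving at 50% coverage is illustration only. II.a is exploratory and the primary endpoint is untouched, but the correction should be made because the error is in the reassuring direction on the study's central safety topic.

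**What to change.** In 9.7.3.4:
1. Align the analysis with 9.1.2: report osteoporosis diagnoses and suspected osteoporotic fractures separately, each with number, percentage and EAIR with 95% CI.
2. Keep all treated women as the denominator for fractures.
3. Report osteoporosis twice: over all women, labelled a lower bound, and among women with at least one on-treatment DXA, noting that the latter may be too high if scanning follows risk.
4. Show beside these figures the number never scanned and scan coverage by risk group, regimen and country.
5. Flag diagnoses in women with no baseline scan recorded in the study, since they may pre-date treatment. A first-ever-scan flag is not feasible as planned: the protocol does not list lifetime DXA history among the data collected.

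The cost is wording and a few more tables; diagnoses, scan dates, risk factors and exposure dates are already collected. The scanned-only figure has a wider CI: for the same proportion, half coverage widens it by 1/√0.5 ≈ 1.4.

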## 8 Research Question and Objectives

Data in patients taking Yselty® in the real-world setting and for more than 1 year is needed to better understand certain safety parameters associated with long-term use. The overall study aim is to assess the long-term safety of Yselty® when used in real life clinical practice.

The primary objective is:

- **I.** To evaluate routinely collected data on long-term safety (>12 months) in relation to BMD with use of Yselty® 200 mg (with ABT) and 100 mg (with and without ABT) dosing regimens.

The exploratory objectives are:

- **II.a** To evaluate the incidence of osteoporosis or fractures suspected to be due to osteoporosis
- **II.b** To evaluate liver enzyme levels above the upper limit of normal and correlated events collected as part of clinical practice
- **II.c** To evaluate any routinely collected clinical data on mood disorders
- **II.d** To evaluate the incidence of uterine endometrial and mammary gland adenocarcinoma
- **II.e** To describe treatment patterns for Yselty® dosing regimens with and without ABT
- **II.f** To evaluate patient adherence to Yselty® treatment
- **II.g** To evaluate any routinely collected clinical data on cardiac disorders indicative for QT interval prolongation
- **II.h** To assess if physicians who prescribe Yselty® follow the summary of product characteristics (SmPC) recommendations including performance of annual dual-energy X-ray absorptiometry (DXA) scans and adherence to the requirement of not prescribing the Yselty® 200 mg regimen without concomitant ABT
- **II.i** To evaluate the incidence of adverse drug reactions (ADRs), serious adverse drug reactions (SADRs) and pregnancies (including pregnancy follow-up)
- **II.j** To evaluate BMD change in patients with routinely collected DXA scans at multiple timepoints to assess mean change of BMD z- and t-scores from baseline or 12-month assessment during long-term (>12 months) use of Yselty®.

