### **11.3 Documentation**

All AEs under exposure to Yselty® that have been reported by the patient to the physician (i.e., AEs, SAEs, ADRs, SADR, special situations) will be documented on the AE Report form in the eCRF/EDC system. Assessment on seriousness and relationship to product, treatment duration, action taken, and outcome of the event will be provided by the treating physician, who will also be responsible for following up on the outcome of SAEs, if this information is not available when first reported. Where required, physicians might be contacted directly, per the MAH's internal follow-up procedure, to obtain further information.

In addition, for selected events (see section 9.4), the MAH will utilise the targeted follow-up questionnaires, where applicable, as per the latest version of the RMP (see section 15.1). The purpose is the ongoing monitoring and safety evaluation of these events.

The documentation of any event within the eCRF ends with the completion of the follow-up of the patient or until it is no longer possible (e.g., lost to follow-up, death, withdrawal). In case of discontinuation of Yselty® for any reason, all events will be collected that occurred up to 30 days after the last administration. Since the  $t_{1/2}$  elimination time of linzagolix is 15 hours, exposure has well ended after 30 days. However, patients who discontinued treatment with Yselty® but experienced BMD decrease or osteoporosis during the study will continue to be followed up unless they have completely withdrawn from the study, and all AEs associated with BMD loss (e.g., osteoporosis, osteopenia, fractures) and all ADRs will be collected irrespective of treatment discontinuation.

All AEs will be summarised in tabulated forms in the interim safety analysis and final study report.

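### Endpoint II.a is an incidence rate of osteoporosis or suspected osteoporotic fracture, but its dedicated analysis counts only women with fractures and uses no person-time

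*Protocol*

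**What the plan says.** Objective II.a in Protocol section 8 is "To evaluate the incidence of osteoporosis or fractures suspected to be due to osteoporosis". Section 9.1.2 makes the endpoint a rate: "Incidence rate of osteoporosis or fractures suspected to be due to osteoporosis". It limits the fractures to minimal-trauma or non-traumatic ones of long bones or spine for which the physician suspects an osteoporotic cause. Section 9.3.6 lists "Osteoporosis diagnoses" as a variable for II.a in its own right, next to the fracture events.

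The dedicated analysis in section 9.7.3.4 is one sentence: "For incidence rates of osteoporosis or suspected osteoporosis-related bone fractures, the number and percentage of patients with fractures will be provided including 95% CIs". It defers nothing to the SAP.

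For liver events the same section provides "the number and percentage of patients with these events and the total number of events as well as the EAIR (exposure adjusted incidence rate"), with 95% CIs. Mood, adenocarcinoma and cardiac events get the same set, and ADRs and SADRs get incidence and EAIR.

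Follow-up is described in several places:
- Section 9.1: recruitment of up to 18 months per country, then observation for as long as is feasible.
- Section 9.5: 20% dropout per year.
- Section 9.2.6: women without BMD decrease or osteoporosis leave observation when they stop treatment. Those with either stay for up to 24 months after the last dose.
- Section 11.3: events are collected for 30 days after the last dose. In the women followed further, bone-related events continue to be collected.
- Section 9.7.2: stratification by dosing regimen and by long- versus short-term use, where numbers allow.

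**The concern.** The analysis sentence departs from its endpoint in two separate ways.

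1. **Numerator.** The endpoint is met by osteoporosis or by a suspected osteoporotic fracture. The analysis counts only women with a fracture.
2. **Measure.** The endpoint is a rate. The analysis is a proportion of patients with no time denominator.

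Bone safety is the study's main subject, and II.a is the clinical counterpart of the primary BMD endpoint. Yet it is the group of incidence-rate events with the least complete analysis.

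A crude proportion mixes risk with length of observation. That matters here because follow-up varies widely and because long- and short-term users differ in exposure time by definition. In addition, the longest post-treatment observation is reserved for women who already have a bone finding.

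**Working it through.** **Text comparison.** This carries the point.

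| Element | Endpoint (9.1.2, 9.3.6) | Dedicated analysis (9.7.3.4) |
|---|---|---|
| Case | Osteoporosis, or suspected osteoporotic fracture | Fracture |
| Measure | Incidence rate | Count and percentage of patients, 95% CI |
| Number of events | Needed if events are to be rated | Not given |
| Person-time | Needed for a rate | Not given |

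**Protocol figures.** None is stated for II.a. The only protocol number used below is the 20% yearly dropout. It is consistent with Table 2: 1,000 × 0.8, 0.8², 0.8³ and 0.8⁴ give 800, 640, 512 and 409.6 (table: 409). The Wald half-width 1.96·√(0.025 × 0.975/n) gives 1.08%, 1.21%, 1.35% and 1.51%, against 1.10%, 1.20%, 1.35% and 1.50% in the table.

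**Person-time (illustration).** Assumptions: 1,000 women, exponential retention with h = −ln 0.8 = 0.223 per year, and uniform entry over 18 months treated as one block. The span from first to last visit is 3.25 to 3.75 years (Q2 2026 to Q3 2029, up to Q1 2026 to Q4 2029). The post-treatment extension is not included. Mean time for a woman with potential follow-up c is (1 − 0.8^c)/h. Averaging c over (span − 1.5, span):

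- span 3.25 years: about 1,904 patient-years (PY)
- span 3.5 years: about 2,044 PY
- span 3.75 years: about 2,176 PY

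**What a percentage does at constant risk.** For 1,000 women with the same potential follow-up, PY = 1,000(1 − 0.8^c)/h, which is 896 at 1 year, 1,613 at 2 years and 2,429 at 3.5 years. The percentage is approximately rate × PY/1,000:

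| Assumed rate per 1,000 PY | 1 year | 2 years | 3.5 years |
|---|---|---|---|
| 2 | 0.18% | 0.32% | 0.49% |
| 5 | 0.45% | 0.81% | 1.21% |
| 10 | 0.90% | 1.61% | 2.43% |

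The ratio from 1 to 3.5 years is 2,429/896 = 2.7 in every row, although the rate is constant.

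**What the numerator does.** Suppose 12 women meet the composite and 2 of them have a fracture; this split is invented. The sentence as written yields 2/1,000 = 0.2% (exact 95% CI 0.02 to 0.72%). The defined endpoint is 12/2,044 PY = 5.9 per 1,000 PY (exact Poisson 95% CI 3.0 to 10.3). Over the range of spans the point estimate runs from 12/2,176 = 5.5 to 12/1,904 = 6.3.

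**Outcome-dependent observation.** Under 9.2.6 and 11.3, time beyond 30 days after the last dose is contributed only by women with BMD decrease or osteoporosis. A single pooled EAIR would mix that selected, probably higher-risk time with on-treatment time. Adding an EAIR is therefore not enough by itself; the two periods need separate numerators and denominators.

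**The case against.** The strongest reply has three parts.

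- **General tables.** Section 9.7.3.5 commits to incidence and EAIR with 95% CIs for all adverse events by system organ class and preferred term, and section 11.3 treats osteoporosis, osteopenia and fractures as such events. This stands, and it bars the reading that osteoporosis without fracture, or person-time, disappears from the report. But a preferred-term table does not form the II.a composite, and it cannot restrict fractures to those of long bones or spine that the physician suspects are osteoporotic.
- **Drafting shorthand.** The sentence opens by naming incidence rates of osteoporosis or fractures, so its ending may be careless wording, and further detail is left to the SAP. That is plausible. But the sentence fixes its output, and an SAP that follows it literally would repeat the mismatch.
- **Status.** The endpoint is exploratory, the study is descriptive, and regimen strata are conditional on numbers. This limits the severity but not the inconsistency.

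Three wider readings are tempting, and the protocol does not support them.

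- **Literature comparison.** A reader might infer that the planned setting against literature is compromised. In section 9.1 that exercise covers BMD results only, in women on add-back therapy from initiation.
- **ECG findings.** A reader might see the same fault here, since the endpoint is an incidence rate and the analysis reads "Number and percentage of patients with QT interval prolongation as reported by physicians following ECG measurement will be evaluated by descriptive statistics". Those findings are classed as adverse events and so fall within the general EAIR tables. The next sentence of 9.7.3.4, on ADRs, also presupposes that incidence rates are presented. Only a clarification is warranted.
- **Pregnancy.** A reader might ask for a pregnancy rate per person-time. Objective II.i promises incidence, not a rate, so that would be a preference.

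**Conclusion.** The point holds for the dedicated II.a analysis: as written, it reports neither the defined case nor the defined measure. It is a contradiction within the protocol and not a detail awaiting the SAP. Importance is moderate: the endpoint is exploratory and the general tables give partial cover, but bone safety is what the study is for.

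The text comparison needs no assumptions. The size does: the 2.7-fold rise rests on 20% yearly dropout and a constant low rate, and the 1,900 to 2,180 PY rest on the entry pattern and span stated above. The event rates and the 12-and-2 split are invented for illustration. The protocol offers no basis for predicting how many osteoporosis diagnoses without fracture would go uncounted.

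**What to change.** Replace the II.a sentence in section 9.7.3.4 so that it gives the number and percentage of patients, the total number of events and the EAIR, each rate and percentage with a 95% CI, for:

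1. osteoporosis or suspected osteoporotic fracture, as defined in 9.1.2;
2. osteoporosis;
3. suspected osteoporotic fracture.

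Define the time at risk. Report treatment plus 30 days separately from later post-treatment follow-up, each with its own events and person-time, and state that the later period covers only women with BMD decrease or osteoporosis.

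Optionally, add a clause that ECG-reported QT prolongation also receives an EAIR, to match its endpoint.

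The cost is a few sentences in 9.7.3.4 and matching table shells in the SAP. Osteoporosis diagnoses, fracture events with the physician's judgement of cause, and treatment start and stop dates are already collected (9.3.4, 9.3.6). No visit or assessment changes.
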